3.7.4 Adverse event of special interest

An adverse event of special interest (AESI) is an adverse event for which on-going monitoring is appropriate within the context of the study. These events necessitate complementary examinations in order to characterize and understand them.

AESIs in this study can be related to:

Hepatotoxicity

Presenting with fatigue, nausea, abdominal pain itching or signs of jaundice such as dark urine, putty or mastic colored stools, jaundice

And/or

ALT or AST >5 x Upper Limit of Normal (ULN) (Patients with normal baseline LFTS)

Or ALT or AST >3 x ULN and total bilirubin >2 x ULN (Potential Hy's Law)

Or ALT or AST >2 x the baseline value if >2 x ULN at baseline

If these occur then a hepatitis panel should be performed

- Hypersensitivity
 - Flushing, appearance of wheals/urticaria, breathlessness, Faintness and/or fall in blood pressure occurring soon after Pyramax administration

The study team, as well as the relevant referral facilities, should be trained to take particular notice of symptoms/signs suggestive of the AESIs in this study.

In case of an AESI confirmed by the study physician, Shin Poong PV shall be informed within 24 hours by fax or email using the contact details above, even if the event does not satisfy any condition of seriousness. Notification will occur through the use of an AESI form.

Note that AESIs should only be reported as a serious adverse event if they fulfill the criteria for seriousness.

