There are limitations to the use of AL which is the commonly used ACT in Nigeria. These include high number of dosing (six) which is not convenient and the need to give the drug with fatty food for optimal absorption of lumefantrine because of its high lipophilic property.[19] Pyronaridine, a Mannich base 1-aza-acridine structurally related to mepacrine and amopyroquine, one of the earliest synthetic antimalarial drugs, was first developed in China over 30 years ago. It has been used as monotherapy in parts of Asia and China.[20] Pyronaridine, is a benzonaphthyridine derivative that is active against *Plasmodium falciparum* and *Plasmodium vivax*.[21, 22]¹⁴

Pyronaridine-Artesunate (PA) is a novel fixed dose ACT drug that received a Positive Opinion through Article 58 from the **European Medicine Agency¹ (EMA)**. This Positive Opinion is a stringent regulatory review and approval granted for a specific group of drugs that will not be marketed in Europe. This rigorous review process is performed in conjunction with the WHO. At the time of the Positive Opinion (registration) PA also obtained WHO prequalification status. Pyramax received approval with EMA for the treatment of acute uncomplicated *P. falciparum* and *P. vivax* malaria. Subsequent EMA approvals have been granted for repeated dosing and for the paediatric formulation of granules in sachets. pyronaridine-artesunate has been found to have good efficacy and tolerability and is cost effective.[23-26] Like DP, pyronaridine-artesunate has a daily dosing regimen and can be taken with or without meals.[23] The studies conducted so far on the efficacy and tolerability of PA showed that other ACTs were not superior to it and there were strong recommendations that PA should be included as a standard antimalarial treatment.[27] The most commonly reported adverse effects were headache, eosinophilia, neutropenia, anaemia, increased platelet count, vomiting, abdominal pain, bradycardia, short lasting transaminase increases and hypoglycaemia.¹⁶ Other studies reported vomiting which may be due to its bitter taste, nausea, loss of appetite and cough.[27] More recent studies provide increasing evidence on the safety of Pyramax.[28, 29]

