3.6.2 Exclusion criteria

- History of allergy to study drugs i.e. artemisinins, lumefantrine and pyronaridine
- Any concurrent illness that could hamper evaluation of response e.g. bacterial infections, viral infections, severe gastrointestinal disease, malnutrition (weight for height $<70\%$)
- Presence of clinical evidence of severe malaria such as prostration, inability to drink or breast feed, persistent vomiting, convulsion, severe anemia hemoglobin <5 g/dl), unarousable coma
- Patients with known chronic diseases like chronic kidney disease, chronic liver disease, malnutrition, cardiac failure, Sickle Cell haemoglobin (HbSS) etc.
- mixed or mono-infection with another Plasmodium species detected by microscopy;
- presence of severe malnutrition defined as a child aged between 6-60 months whose weight-for-height is below -3 z-score, or has symmetrical edema involving at least the feet or has a mid-upper arm circumference <115 mm)
- Parent or guardian who in the judgment of the investigator will not comply with protocol in the opinion of the investigator

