- **Gametocyte carriage**: proportions of patients with gametocyte at a given point in time using the Area Under the Curve Graph for PA will be compared with that of AL.

3.7.3 Safety parameters will be evaluated as follows:

- Safety will be analyzed in terms of adverse events and severe adverse events using clinical signs, symptoms and laboratory parameters.
- Liver enzymes (ALT/AST) >3 times upper limit of normal (ULN) plus peak total bilirubin >2 times ULN in the absence of a significant alkaline phosphatase increase (= Hy's law) will be deemed as serious adverse effects (SAE).
- ALT and AST >5 times ULN will be deemed an AESI. (see below)

Serious Adverse Events

An adverse event will be considered serious if it fulfils one of the following criteria:

- causes death or
- is life-threatening or necessitates hospitalization or prolongs hospitalization or results in persistent or significant disability/incapacity or is a medically important event constitutes a possible Hy's Law

An example of an important medical event is one that while not-immediately life-threatening might become so if there had been no intervention

In case of SAEs, independent of causality, the healthcare personnel must immediately contact the PI / Investigator for validation of the seriousness and determination of the causality.

Subsequently, the procedure described below must be followed:

- SEND (within 24 hours and pdf scanned documents) the signed and dated copy of the “Adverse Event form” and the form “SAE complementary information” to Shin Poong Pharmacovigilance (PV) (Tel/[contact] or email: [contact])
- Contact immediately (the same day) the medical monitor/Pyramax QPPV responsible for safety in case of death or life-threatening events.
- The follow-up of each fatal or life-threatening AE must be provided to the medical monitor and Shin Poong PV within the same timeline as the initial report (within 24 hours and preferably by email).
- ATTACH to the Case Record Form (CRF) the photocopy of all available results and examinations which were undertaken (and their date). Analysis results must be accompanied by the laboratory normal ranges. Special consideration shall be taken to ensure patient anonymity, and to the correct completion of the patient’s study specific identifier in the copies of the source documents provided to the sponsor.

Causality

All adverse events must have causality assigned by the investigator. As a guide causality can be assigned as follows:

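### Section 3.7.4 has no enzyme-only liver AESI trigger for a child whose baseline LFTs are not all normal but whose Day 0 ALT and AST are both at or below 2 x ULN, and section 3.7.3 does not clearly fill the gap

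*Combined protocol and SAP*

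**What the plan says.** Section 3.7.4 lists the laboratory findings that make a liver event an AESI. Two depend on enzymes alone:

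- "ALT or AST >5 x Upper Limit of Normal (ULN) (Patients with normal baseline LFTS", a line limited to children with normal baseline tests.
- "Or ALT or AST >2 x the baseline value if >2 x ULN at baseline", a line limited to children already well above normal.

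A third line needs an enzyme above 3 x ULN together with total bilirubin above 2 x ULN. A list of symptoms and signs is joined to the laboratory lines by 'and/or', so it can qualify a child without them. Two actions follow: "If these occur then a hepatitis panel should be performed", and, once the study physician confirms the AESI, "Shin Poong PV shall be informed within 24 hours by fax or email". The notice is due whether or not the event is serious.

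Section 3.7.3 states the rule separately: "ALT and AST >5 times ULN will be deemed an AESI". It sets no baseline condition and points the reader forward to 3.7.4. The bullet before it treats as serious "Liver enzymes (ALT/AST) >3 times upper limit of normal (ULN) plus peak total bilirubin >2 times ULN", provided alkaline phosphatase is not significantly raised.

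On entry, section 3.6.2 excludes "Patients with known chronic diseases like chronic kidney disease, chronic liver disease, malnutrition" and other conditions, but sets no ALT or AST limit. Liver tests are scheduled on Days 0, 3, 7 and 28.

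**The concern.** The two enzyme-only lines in 3.7.4 do not meet. One stops where baseline LFTs cease to be normal. The other starts only above 2 x ULN. A mildly raised baseline lies between them, and such a child can be enrolled.

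This matters because liver injury is a named AESI in this trial. The Background section lists "short lasting transaminase increases and hypoglycaemia" among the test drug's most commonly reported adverse effects. An isolated enzyme rise without symptoms is what a laboratory-only trigger is there to catch. If the trigger does not apply, neither the hepatitis panel nor the 24-hour AESI notice is required. A mildly raised baseline would then get less scrutiny than either a normal one or a higher one, and the protocol gives no reason for that ordering.

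**Working it through.** The plan states no figure to reproduce here. The check applies the written rules to specific values.

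**Inputs** (Table of Normal Values): ULN is 40 IU/L for ALT, 37 IU/L for AST and 1.0 mg/dl for total bilirubin.

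- 2 x ULN: ALT 2 x 40 = 80; AST 2 x 37 = 74.
- 5 x ULN: ALT 5 x 40 = 200; AST 5 x 37 = 185.
- 2 x bilirubin ULN: 2.0 mg/dl.

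**The band.** With neither enzyme above 2 x ULN, the uncovered Day 0 values are ALT 41-80 or AST 38-74. If one enzyme is in the band and the other is above 2 x ULN, the >2 x baseline line can still fire through the higher one, so that child is not wholly uncovered. The Summary of Activities counts bilirubin and alkaline phosphatase among the liver function tests. Read strictly, a child with normal enzymes but one of those out of range also lacks normal baseline LFTs and has no enzyme-only trigger.

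**Worked case, 3.7.3 read literally as 'and'.** Day 0 AST 30, later AST 120; ALT peak 400 (10 x ULN); bilirubin not above 2.0 mg/dl; no listed symptom.

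| Day 0 ALT | >5 x ULN line (3.7.4) | >2 x baseline line (3.7.4) | 3.7.3 as 'and' | AESI? |
|---|---|---|---|---|
| 30, all LFTs normal | 400 > 200: fires | baseline not above 80 | AST 120 not above 185 | Yes |
| 60 | baseline not normal | baseline not above 80 | AST 120 not above 185 | No |
| 81 | baseline not normal | 400 > 162: fires | AST 120 not above 185 | Yes |
| 199 | baseline not normal | 400 > 398: fires | AST 120 not above 185 | Yes |

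Every Day 0 ALT from 41 to 80 behaves like 60. If AST instead peaks at 190 (above 185), both enzymes exceed 5 x ULN and 3.7.3 catches all four rows.

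**Mirror case.** Day 0 ALT 30, later ALT 120; AST peak 370 (10 x ULN). From Day 0 AST 38-74 this is not an AESI on the literal reading.

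**3.7.3 read as 'or'.** ALT 400 > 200 is enough alone, and so is AST 370 > 185. Every case above is an AESI. What remains is that 3.7.3 ignores baseline while 3.7.4 makes the same threshold depend on it.

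**Wider check.** In 6,480 combinations with at least one Day 0 enzyme above 1 and up to 2 x ULN, neither above 2 x ULN, and bilirubin not raised, no 3.7.4 enzyme-only line fired, even at 50 x ULN. The literal 3.7.3 sentence fired in 1,620, all with both enzymes above 5 x ULN. These are counts of grid points, not frequencies in patients.

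**The case against.** The strongest reply is that the 'and' in 3.7.3 is loose drafting. The sentence refers forward to 3.7.4, where all three laboratory lines say 'or', and the bullet before it in 3.7.3 writes the enzymes with a slash. No other line requires both. On that reading no child above 5 x ULN is missed. This largely stands: 'or' is the likelier intention. It does not remove the need for an edit, because the forward reference can equally be taken to make the baseline restriction in 3.7.4 govern.

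There are also backstops. Listed symptoms qualify at any baseline, and so does the bilirubin line. An event judged medically important is serious under 3.7.3 and goes to the same pharmacovigilance unit within 24 hours. Section 3.7.5 requires follow-up of laboratory adverse events. These points stand, although the serious-event route is a matter of judgement.

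A reader might infer that children with mildly raised enzymes have no liver monitoring, or that the trial will lose hepatotoxicity data. The documents do not support that: the same liver tests are taken from every child, and only the AESI classification and its two actions are in question.

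A narrower edit would extend the >5 x ULN line in 3.7.4 to baselines up to 2 x ULN. It closes the band. If 3.7.3 stays without a condition, however, the conflict remains. If 3.7.3 is given the same condition, a child with Day 0 ALT and AST both 150 and later both 250 would no longer be flagged. That child is caught today by 3.7.3 (250 > 200 and 250 > 185), but not by the >2 x baseline line (250 < 300).

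**Conclusion.** The point holds as a minor defect of wording. Section 3.7.4 leaves a definable group of enrollable children without an enzyme-only trigger. Section 3.7.3 either covers only those with both enzymes above 5 x ULN or contradicts 3.7.4 on baseline. Actual missed AESIs depend on the literal 'and', which is the less likely reading. Even then they are limited to rises in which the two enzymes are not both above 5 x ULN, no listed symptom is present and bilirubin is not above 2.0 mg/dl.

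Two assumptions matter. Normal is taken from the protocol's own table; an investigator who counted mild elevations as normal would close the gap, but the text does not say so. The flagged result from Day 0 ALT 0-40 requires the other baseline liver tests to be normal too. The documents do not say how many children fall in the band, so frequency cannot be estimated; missed events are probably rare.

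**What to change.** In 3.7.4, delete the parenthesis restricting the >5 x ULN line to normal baseline LFTs, so that ALT or AST above 5 x ULN is an AESI at any baseline. Keep the bilirubin line and the >2 x baseline line as additional triggers. In 3.7.3, change 'and' to 'or' and leave it without a baseline condition.

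Both edits only widen the rule, so every child flagged now stays flagged. They use the liver tests already scheduled.

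The cost is a few more AESI notices and hepatitis panels. A child already above 5 x ULN at Day 0 (ALT above 200 or AST above 185) could be flagged with no further rise. The >2 x baseline line would then lower the threshold only for Day 0 ALT of about 81-99 (2 x 81 = 162 to 2 x 99 = 198, against 200) and Day 0 AST of about 75-92 (150 to 184, against 185). Above those values, 5 x ULN becomes the lower threshold. The sponsor should accept that shift knowingly, since it gives less weight to the baseline-relative rule.

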3.7.5 Follow-up of Adverse Events

The healthcare personnel must take all appropriate measures to protect the safety of the patients. Personnel must ensure to document follow-up of the evolution of each adverse event (clinical, biological or other) until resolution or until the stabilization of the patient's status.

All new relevant information concerning the initial SAE shall be recorded on a form "SAE follow-up information form" by the nursing staff of the health centre, and shall be validated by the PI/co-PI who shall transfer the form to the local person/physician responsible for the pharmacovigilance of the project and Shin Poong PV.

In case of a serious adverse event the patient must be followed until complete resolution and normalization of all analysis results, or until chronicity of the patient's status. This can imply that the follow-up of the patient must continue beyond the period of follow-up per protocol, and that additional investigations could be requested.

DATA ANALYSIS.

Data will be entered into the computer using the Epi-data software. This subsequently would be cleaned and transferred to SPSS Statistic Software version 20 for analysis. The outcome of interest (dependent variable) presented as a categorical variable with, presence of malarial parasitemia, and the level of efficacy reported. The independent or explanatory variable of interest in this study would be use of chemotherapy. All independent variable would be reported as categorical. Proportions of treatment outcome will be compared by using chi square. Normally distributed continuous data will be compared using unpaired student t-test. Mean values will be given as mean \pm SD and values of $P < 0.05$ will be considered statistically significant.

ETHICAL CONSIDERATIONS

This study, will be a prospective randomized open label clinical trial comparing the safety and efficacy of Pyronaridine-artesunate and Artemether-lumefantrine in the treatment of symptomatic acute uncomplicated malaria in Nigerian children aged 3 to 144 months who seek treatment in the study hospital. The studies will be conducted according to Good Clinical Practice and the Declaration of Helsinki.

Confidentiality of data: Personal details of enrollees in the study will be treated with utmost confidentiality, as it is against the principles of good clinical practice to make such information public. Also, codes will be assigned to all participants.

Translation of the informed consent to the local language: The informed consent has been translated to Yoruba (the local language) and is attached. Translation will has been verified for consistency and accuracy by an independent translator. The consent form will include the purpose of the study, risks and benefits to participants, confidentiality and voluntariness.

Beneficence to Enrollees: Enrollees in this study will have the advantage of been treated for malaria and any related febrile illnesses with no cost. Also, findings in the study will be useful in monitoring artemisinin resistance in Nigeria.

Non-maleficence to Enrollees: There is little or no risk involved in this study. Blood samples that will be collected from the prospective arm of the study will be via venipuncture technique which will be done by a qualified medical officer. The participant will only feel a mild pain and there may be a bruise which will go away in a few days.

Voluntariness: Enrollees in the study are absolutely free to decline or withdraw from the study without jeopardy and without loss of benefits to which they are entitled.

Summary of Activities

| ACTIVITY | Day 0 | Day 1 | Day 2 | Day 3 | Day 7 | Day 14 | Day 21 | Day 28 | Extra Visit | Extra Visit |
|---|-------|-------|-------|-------|-------|--------|--------|--------|-------------|-------------|
| Demographic data and clinical assessment | X | X | X | X | X | X | X | X | X | X |
| Blood smear – (Thick & Thin) | X | X | X | X | X | X | X | X | X | X |
| Blood spot on filter paper (for PCR) | X | X | X | X | X | X | X | X | X | X |
| Haematocrit | X | X | X | X | X | X | X | X | X | X |
| Full blood count | X | ✖ | ✖ | X | X | | | X | | |
| Blood Chemistry – Creatinine & Random Blood glucose | X | | | X | X | | | X | | |
| Liver Function test- AST, ALT, Bilirubin & Alkaline Phosphate | X | | | X | X | | | X | | |
| Adverse events recording | X | X | X | X | X | X | X | | | |
| Concomitant treatments recording | X | X | X | X | X | X | X | X | X | X |
| Study medications (AL or PA) | X | X | X | | | | | | | |

CASE RECORD FORM

**COMPARATIVE EFFICACY AND SAFETY OF PYRONARIDINE-
ARTESUNATE VERSUS ARTEMETHER-LUMEFANTRINE IN THE
TREATMENT OF Malaria AMONG CHILDREN IN SOUTH-WEST
NIGERIA**

PYRONARIDINE-ARTESUNATE VERSUS ARTEMETHER-LUMEFANTRINE STUDY

Study ID- PAAL:

Study ID: Hosp.No: Date of enrollment:

Sex: Age (months):

Date of birth/...../..... Weight (kg): Height (CM):

Temp (oC): Phone no:

Address (+ brief description):
.....
.....
.....

Symptoms History

Record duration of symptoms in days (Today = 1) Fever: () Vomiting: () Chills & rigors ()

Diarrhoea: () Headache: () Abdominal pains: () Irritability: () Loss of appetite ()

Other complaint 1: Other complaint 2:

Past medical history:

History of drug allergy: (Yes/No) If yes, name of drug:

Any other relevant history 1:

Any other relevant history 2:

Treatment history: Has the child received any of the following drugs in the last 2 weeks (Yes/No)

CQ () SP () PCM () ACT () Specify.....

Antibiotic () Specify..... Other:

Clinical examination:

General: Palor (Yes/No) Icterus (Yes/No) Fever (Yes/No) Dehydration (Yes/No)

CVS: Pulse/min..... Apex Beat..... Heart sounds.....

Respiratory system: Resp. rate..... Breath sound.....

Abdomen: Liver size (Below costal margin)..... Spleen size..... Kidneys.....

Muscle tone: (1) Normal (2) Hypotonia (3) hypertonia Eyes: conjunctivitis/Discharge (Yes/No)

Ears: Discharge (Yes/No)

MP result: PCV.....

**PYRONARIDINE-ARTESUNATE VERSUS ARTEMETHER-
LUMEFANTRINE STUDY**

Study ID- PAAL:

Study ID -----

Study Drug Schedule

| Study Day | Date | Drug [PA or AL] Name of Drug | Dose | Time Drug Given |
|------------------|-------------|---|-------------|------------------------|
| Day 0 | | | 1st | |
| | | | 2nd | |
| Day 1 | | | 1st | |
| | | | 2nd | |
| Day 2 | | | 1st | |
| | | | 2nd | |

Comments:

Any vomiting? Yes/No

Time

Any Redosing?

Time

Any vomiting? Yes/No

Any other comments

CLINICAL FOLLOW UP RECORD

| | D0 | D1 | D2 | D3 | D7 | D14 | D21 | D28 | Day 35 | Day 42 | Other visit |
|---------------------------|-----------|-----------|-----------|-----------|-----------|------------|------------|------------|---------------|---------------|--------------------|
| Date | | | | | | | | | | | |
| Temp (°C) | | | | | | | | | | | |
| Pallor | | | | | | | | | | | |
| Jaundice | | | | | | | | | | | |
| HR/Pulse Rate | | | | | | | | | | | |
| Resp Rate | | | | | | | | | | | |
| Lung Fields | | | | | | | | | | | |
| Liver (cm) | | | | | | | | | | | |
| Spleen (cm) | | | | | | | | | | | |
| Weight (kg) | | | | | | | | | | | |
| PCV (%) | | | | | | | | | | | |
| Parasite Density/ μ L | | | | | | | | | | | |
| Gametocyte Count/ μ L | | | | | | | | | | | |

TREATMENT EMERGENT SIGNS AND SYMPTOMS (TESS)

| Features | Day 0 | | Day 1 | | Day 2 | | Day 3 | | Day 7 | | Day 14 | | Day 21 | | Day 28 | | Day 35 | | Day 42 | | Extra Visit | | Extra Visit | | |
|---------------|-------|---|-------|---|-------|---|-------|---|-------|---|--------|---|--------|---|--------|---|--------|---|--------|---|-------------|---|-------------|---|--|
| | P | S | P | S | P | S | P | S | P | S | P | S | P | S | P | S | P | S | P | S | P | S | P | S | |
| Date | | | | | | | | | | | | | | | | | | | | | | | | | |
| Chills/Rigors | | | | | | | | | | | | | | | | | | | | | | | | | |
| Fever | | | | | | | | | | | | | | | | | | | | | | | | | |
| Anorexia | | | | | | | | | | | | | | | | | | | | | | | | | |
| Nausea | | | | | | | | | | | | | | | | | | | | | | | | | |
| Vomiting | | | | | | | | | | | | | | | | | | | | | | | | | |
| Diarrhoea | | | | | | | | | | | | | | | | | | | | | | | | | |
| Abd. Pains | | | | | | | | | | | | | | | | | | | | | | | | | |
| Cough | | | | | | | | | | | | | | | | | | | | | | | | | |
| Palpitation | | | | | | | | | | | | | | | | | | | | | | | | | |
| Insomnia | | | | | | | | | | | | | | | | | | | | | | | | | |

Present (P): 0 = Not present, 1= Present, 2 = Not evaluable

Severity (S): 1 = Mild 2 = Moderate 3 = Severe

TREATMENT EMERGENT SIGNS AND SYMPTOMS (TESS)

| Features | Day 0 P S | | Day 1 P S | | Day 2 P S | | Day 3 P S | | Day 7 P S | | Day 14 P S | | Day 21 P S | | Day 28 P S | | EXTRA VISIT | |
|-------------|-----------------|--|-----------------|--|-----------------|--|-----------------|--|-----------------|--|------------------|--|------------------|--|------------------|--|----------------|--|
| Date | | | | | | | | | | | | | | | | | | |
| Pallor | | | | | | | | | | | | | | | | | | |
| Yellow eyes | | | | | | | | | | | | | | | | | | |
| Headaches | | | | | | | | | | | | | | | | | | |
| Rash | | | | | | | | | | | | | | | | | | |
| Reflex | | | | | | | | | | | | | | | | | | |
| Diplopia | | | | | | | | | | | | | | | | | | |
| Fatigue | | | | | | | | | | | | | | | | | | |
| Other | | | | | | | | | | | | | | | | | | |
| Other | | | | | | | | | | | | | | | | | | |

Present (P): 0 = Not present, 1= Present, 2 = Not evaluable

Severity (S): 1 = Mild 2 = Moderate 3 = Severe

.....
LABORATORY RESULTS: LFT & BLOOD CHEMISTRY

| PARAMETER | DAY 0 | DAY 3 | DAY 7 | DAY 27 | DAY 35 | DAY 42 |
|----------------------|-------|-------|-------|--------|--------|--------|
| Date | | | | | | |
| Urea | | | | | | |
| Creatinine | | | | | | |
| Random Blood sugar | | | | | | |
| Total bilirubin | | | | | | |
| Conjugated bilirubin | | | | | | |
| ALT | | | | | | |
| AST | | | | | | |
| ALP | | | | | | |
| GGT | | | | | | |

LABORATORY RESULTS: HAEMATOLOGY

| PARAMETERS | D0 | DAY 3 | DAY7 | D28 | EXTRA VISIT | EXTRA VISIT |
|------------------------|----|-------|------|-----|-------------|-------------|
| White blood cell count | | | | | | |
| Eosinophils | | | | | | |
| Platelet count | | | | | | |
| Neutrophils | | | | | | |
| Basophils | | | | | | |
| Lymphocytes | | | | | | |
| | | | | | | |

ADVERSE EVENTS RECORD

| ADVERSE EVENT | DAY 0 | DAY 3 | DAY 7 | DAY 28 | EXTRA VISIT | EXTRA VISIT |
|-----------------------------|--------------|--------------|--------------|---------------|--------------------|--------------------|
| | | | | | | |
| | | | | | | |
| | | | | | | |
| | | | | | | |
| | | | | | | |
| | | | | | | |
| | | | | | | |

SUMMARY: EFFICACY

: D14 [], D21 [], D28 []. {ETF = 1, LPF = 2, LCF = 3, ACPR = 4, Withdrawn = 5, Lost to follow up = 6}

| Treatment outcome | ETF | LPF | LCF | ACPR | WITHDRAWN | LOST TO FOLLOW UP |
|-------------------------|-----|-----|-----|------|-----------|-------------------|
| Day 7 | | | | | | |
| Day 14 | | | | | | |
| Day 21 | | | | | | |
| Day 28 | | | | | | |
| Day 35 | | | | | | |
| Day 42 | | | | | | |
| Extra visit (Date-----) | | | | | | |
| Extra visit (Date-----) | | | | | | |

**PYRONARIDINE-ARTESUNATE VERSUS ARTEMETHER-
LUMEFANTRINE STUDY**

Study ID- PAAL:

Enrollee's Initials

STUDY OUTCOME

- 1. COMPLETED**
- 2. LOST TO FOLLOW UP**
- 3. WITHDRAWAL OF INFORMED CONSENT**
- 4. PROTOCOL VIOLATION**

STUDY CONCLUSION

- 1. ACPR**
- 2. LPT**
- 3. LCF**
- 4. ETF**

Investigator - Name

Signature & Date

Principal investigator - Name

Signature & Date

REFERENCES

1. World Health Organisation: In *Guidelines for the Treatment of Malaria (3d Edition)*, 3rd edition. Geneva2015.
2. World Health Organisation: **World Malaria Report 2016**. Geneva: Licence: CC BY-NC-SA 3.0 IGO; 2016.
3. FMOH: *National Malaria Strategic Plan 2014-2020*. Abuja, Nigeria: Federal Ministry of Health, Nigeria; 2014.
5. World Health Organisation: **World Malaria Report 2017**. Geneva: License: CC BY-NC-SA 3.0 IGO; 2017.

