attachment)

Where

$Z_{1-\alpha}$ = standard normal deviate for level of significance; at $\alpha=0.05$, it is 1.96

$Z_{1-\beta}$ = standard normal deviate for power (1- β); at $\beta=0.2$ (80% power), it is 0.84 but at $\beta=0.1$ (90%), it is 1.28

P_1 : 28-day cure rate in AL = 96.4%

P_2 : 28-day cure rate in PA = 98.9%

ε : non-inferiority margin= 5%

Applying the formula and parameters above, sample size for each group

90% power: 70 per group [total 140]

80% power: 51 per group [total 102]

Assuming a difference of 2.5% in cure rate between PA and AL (98.9% vs 96.4%) [REF- Roth et al, 2018], 140 patients are required to be 90% sure that the upper limit of a one-sided 95% confidence interval will exclude a difference in favor of the standard group of more than 5%

Total N = 140. Allowing for 20% loss to follow up, the total number of patients required would be 168 to give 84 patients per arm. (See sample size calculation attachment)

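### The trial is sized to show non-inferiority within 5 points, but the only planned comparison of treatment outcome is a chi-square test, which cannot show it

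*Combined protocol and SAP*

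**What the plan says.** Section 3.6 (Sample Size Calculation) is a non-inferiority calculation. It gives "non-inferiority margin= 5"%, "28-day cure rate in AL = 96.4"% and "28-day cure rate in PA = 98.9"%. It justifies 140 patients by this target, with 90% power: "the upper limit of a one-sided 95% confidence interval will exclude a difference in favor of the standard group of more than 5"%. After an allowance for loss to follow-up, the total is 168, or 84 per arm.

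The Data Analysis section (unnumbered, after Section 3.7.5) is the only analysis plan. For treatment outcome it says "Proportions of treatment outcome will be compared by using chi square". It adds the unpaired t-test for normally distributed continuous data, and P values under 0.05 "will be considered statistically significant". It gives no margin, confidence interval for a difference, non-inferiority hypothesis or decision rule.

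The Study Design section makes PCR-adjusted adequate clinical and parasitological response to day 28 the primary outcome. The objectives in Sections 2 and 2.1 speak only of comparing the two drugs.

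**The concern.** The two sections answer different questions. Section 3.6 asks whether PA can be shown to be no more than 5 points worse than AL. Chi-square asks whether the data are incompatible with equal cure rates. In a trial of this size with cure rates near 100%, failing to reject equality is the usual result whether or not PA is acceptable.

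Followed as written, the most likely primary result is a statement of no significant difference. The Rationale presents the trial as support for wider use of PA in Nigeria, so that statement would probably be taken to mean that PA is as good as AL. Nothing in the analysis would limit the chance of reaching that reading with an inferior drug. If the sponsor instead recalls the confidence-limit criterion at analysis, the interval method will be chosen after the data of an open-label trial are known.

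A lesser point is that very few failures are expected, so the large-sample approximation behind chi-square is weak.

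**Working it through.** **Inputs, all from Section 3.6.** P1 (AL) = 0.964; P2 (PA) = 0.989; margin 0.05; one-sided 95% limit; 70 per group for 90% power and 51 for 80%; 84 per arm after inflation.

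**1. Reproducing the plan's sample size.** With the plan's formula:

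n = (z_alpha + z_beta)² × [P1(1−P1) + P2(1−P2)] / [margin − (P1−P2)]²

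- Variance term: 0.964×0.036 + 0.989×0.011 = 0.034704 + 0.010879 = 0.045583
- Denominator: (0.05 + 0.025)² = 0.005625
- 90% power, z_alpha = 1.645: (1.645 + 1.28)² × 0.045583 / 0.005625 = 69.3, so 70
- 80% power, z_alpha = 1.645: (1.645 + 0.84)² × 0.045583 / 0.005625 = 50.0 (50.04), so 51

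Both figures match. The 90% is thus the power of a one-sided 5% non-inferiority test. (The z of 1.96 printed in Section 3.6 gives 86 and 64, which do not match. That is a separate error.)

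**2. Expected failures at the planning rates.**

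| Per arm | AL | PA | Mean per failure cell |
|---|---|---|---|
| 70 | 70×0.036 = 2.5 | 70×0.011 = 0.8 | 1.6 |
| 84 | 84×0.036 = 3.0 | 84×0.011 = 0.9 | 2.0 |

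The usual minimum expected count for chi-square is 5. As an illustration, 0 PA and 4 AL failures at 84 per arm give P = 0.043 by chi-square and P = 0.121 by Fisher's exact test.

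**3. Behaviour of the two rules.** Every pair of failure counts was enumerated and weighted by its two binomial probabilities, with AL at 96.4%. Chi-square is Pearson's at the two-sided 5% level. The confidence-limit rule passes PA if the one-sided 95% Newcombe upper limit for AL minus PA is below 5 points.

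| True PA cure | n per arm | Chi-square not significant (continuity-corrected) | Newcombe rule declares non-inferiority |
|---|---|---|---|
| 98.9% (planning) | 70 | 88% (98%) | 86% |
| 98.9% | 84 | 85% (96%) | 90% |
| 91.4% (at the margin) | 70 | 77% (88%) | 4.7% |
| 91.4% | 84 | 75% (84%) | 4.5% |
| 86.4% (10 points worse) | 70 | 41% (55%) | 0.3% |
| 86.4% | 84 | 34% (47%) | 0.2% |

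At the planning rates chi-square is therefore significant in only 12% of trials at 70 per arm and 15% at 84. A simple Wald limit, the form implied by the sizing formula, has power of 93% and 96% there, but passes PA at the margin in 7.1% and 6.5% of trials, above the nominal 5%.

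**4. One concrete result.** Take 84 per arm with 6 PA and 2 AL failures.

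- Chi-square = 2.1, P = 0.15: no significant difference.
- Cure: AL 82/84 = 0.9762 (Wilson upper limit 0.9921); PA 78/84 = 0.9286 (Wilson lower limit 0.8678); difference 0.0476.
- Newcombe upper limit: 0.0476 + √(0.0159² + 0.0608²) = 0.0476 + 0.0628 = 0.110.

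The upper limit is about 11 points, more than twice the margin.

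**The case against.** The strongest reply is that the criterion is already in the protocol. Section 3.6 states the margin, the limit and the direction, and the Data Analysis sentence is generic and does not name the primary outcome. Nor does any section say that P above 0.05 means equivalence, so 77% and 41% are not error rates of a stated rule. They measure what a common misreading would cost. Both points are fair. But Section 3.6 only justifies the sample size, names no interval method, and is contradicted by the one section that says how outcomes will be compared. An analyst following the plan would run chi-square.

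Other parts of the reply stand as qualifications:

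- The uncorrected chi-square is conservative here. Its exact size with both arms at 96.4% is 4.5% at 70 per arm and 4.4% at 84. The sparse counts make the approximation poor but do not inflate type I error.
- A significant chi-square favouring PA would imply non-inferiority. Every such table at 70 and 84 per arm also met the Newcombe limit. The weakness is that it happens in only about 12–15% of trials at the planning rates.
- The objectives never mention non-inferiority, so they need editing as well as the analysis sentence.

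**Conclusion.** The concern holds and must be fixed before analysis. As written, the plan cannot answer the question the trial was sized for. If PA were exactly 5 points worse, the planned test would show no significant difference in 75–77% of trials (84–88% with continuity correction), against about 4.5–4.7% false passes for a Newcombe limit. If the planning rates are right, chi-square would be significant in 12–15%, while the confidence-limit rule would succeed in 86–90%. Planned enrolment of 84 per arm does not change the conclusion.

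These figures assume that AL cures 96.4%, that arms are equal, that 70 to 84 children per arm are evaluable, and that the cure rates in Section 3.6 refer to the PCR-adjusted outcome, which that section does not say. Unadjusted failures could be more numerous, which would ease the sparse-count problem for that outcome but not the mismatch of question.

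**What to change.** For the primary outcome, replace the chi-square sentence with a rule on these lines:

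> The difference in day-28 PCR-adjusted cure (AL minus PA) will be estimated with a one-sided 95% upper confidence limit by the Newcombe method. PA will be declared non-inferior only if this limit is below 5 percentage points.

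Miettinen-Nurminen would also serve. Name one method in advance. Keep Fisher's exact test or chi-square for secondary comparisons of difference only.

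In the same edit:

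- State non-inferiority in the primary objective.
- Name the analysis population and how withdrawn and lost children are counted.
- Settle the confidence level by correcting the printed z of 1.96. If a one-sided 97.5% limit is really meant, the plan's formula needs 86 per arm for 90% power, and Newcombe power at the planning rates falls to 63% at 70 per arm and 76% at 84.

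The cost is a few lines of text and no extra data. The price in power is modest: at one-sided 5%, the Newcombe limit gives 86% at 70 evaluable per arm instead of the stated 90%, and reaches 90% only if all 84 per arm are evaluable.
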